### **Aim 3**

All data used in Aim 3 come from literature, our previously published studies, and data collected in Aim 2 and Aim 3. For example, CASI and DARE results will provide data on screening test characteristics, screening test costs, and quality of life scores. The parameters required to structure the decision-analytic model will be derived from these sources.

For comparative cost-effectiveness analysis, we will consider these strategies: no screening, ASE, ACE, and clinician DARE. In addition, we will evaluate the optimal interval for performing these tests (annual, biennial, or triennial) and optimal age to initiate training MSM to perform the test.

For the analysis, we will develop an individual-level state-transition (i.e., micro-simulation) model (STM). They also enable screening interval evaluation, and appropriate screening ages. The model will be programmed in TreeAge Pro 2016 software (TreeAge Software, Inc., Williamstown, MA).

The starting (hypothetical) cohort will be comprised of MSM in the US distributed in health states based on the baseline prevalence of anal HPV infection and anal dysplasia among HIV-positive persons. Patient profiles will be defined based on history/diagnosis of anal abnormalities, HIV disease status (i.e., current and nadir CD4 count of CD4>500, CD4 200-500, or CD4<200), HPV vaccination status, and receipt of antiretroviral therapy (yes or no). We identified these characteristics as they might impact long-term outcomes including survival, quality-adjusted life years (QALYs), and anal cancer mortality risk. Baseline age will be assigned according to the age distribution of MSM in the US. The cycle length (i.e., the amount of time represented by each model simulation step) will be 12 months which seems appropriate (1) since persons in our pilot study were willing to screen at least every few months, (2) given recommendations of an annual DARE, and (3) given a higher likelihood that more frequent exams will detect anal tumors at an earlier stage.

Health quality of life scores will be assigned for each health state using utility scores (i.e., quality of life weights) ranging from 0.0 to 1.0. This assignment will be computed as the mean EQ-5D score associated with each participant who is classified in each health state.

Cost-effectiveness using societal- and health care-sector perspectives will be evaluated in terms of incremental cost-effectiveness ratios (i.e., the ratio of difference in costs between 2 alternatives to the difference in effectiveness between the same 2 alternatives), comparing each strategy in sequence from lowest expected cost to most expensive. Issues of strong and weak dominance of clinical strategies will be considered. We will use the commonly accepted willingness-to-pay (WTP) threshold of \$100,000/QALY to determine the most-cost-effective strategy. As per the guidelines from the second panel on cost-effectiveness analysis, we will also estimate net monetary benefits (i.e., the linear combination of costs and effects expressed in US dollars). Other long-term health outcomes will be estimated in terms of lifetime risk of developing anal cancer among individuals who performed ASE or ACE relative to no screening, lifetime anal cancer mortality risk among those individuals, and life expectancy gained attributed to screening using anal examinations.

To evaluate robustness of the outcomes, we will perform comprehensive sensitivity analysis on all model parameters. We will perform one-way sensitivity analyses, varying model parameters (e.g., screening accuracy, treatment efficacy, costs, etc.) to look for consistent patterns in the results. Decision uncertainty will be evaluated using probabilistic sensitivity analysis (PSA). For PSA, we will perform 10,000 runs of Monte Carlo simulation using two nested simulation loops where the inner loop will evaluate the outcomes across the simulated population and the outer loop will sample those parameters to reflect the uncertainty in the model parameters. The outcomes of PSA will be presented in the form of a cost-effectiveness acceptability curve, which plots the probability that an intervention is cost-effective against various willingness-to-pay thresholds.

Exploratory analysis of de-identified data may also be done by collaborators including the Medical University of South Carolina. The Safe Harbor method will be used to de-identify the data <https://www.hhs.gov/hipaa/for-professionals/privacy/special-topics/de-identification/index.html#standard>.

## **PROTOCOL FIDELITY AND QUALITY CONTROL**

Protocol activities will be documented with a checklist. To ensure identical protocols in each location, qualified clinicians will conduct clinical exams of participants after being trained in the

study protocol by [name] and after being trained in the study's clinical procedures by either [name], [name], [name], or Nurse Practitioner [name].

At study start and semi-annually, the PI will observe all procedures for two individuals in both Houston and Chicago sites and provide critique to prevent drift in study protocol. Houston co-I [name] and Chicago co-I [name] will attend five initial Visit 1 appointments in Houston and Chicago, respectively, to observe the clinician's DARE technique and protocol.

To document the repeatability of the NP DARE results (which was 95% in the pilot), a second clinician at each clinic will perform a second DARE on ~40% of persons in each study site in the first six months of enrollment (i.e., 40 in each city). The secondary NPs will also be trained in study protocol and DARE.

## **HUMAN PROTECTIONS**

### **Overview**

The principles of Institutional Review Board (IRB) approval and informed consent described in the Food and Drug Administration (FDA) regulations (21 CFR Part 50 and 56) and Department of Health and Human Services (DHHS) regulations for the Protection of Human Subjects regulations (45 CFR Part 46) must be followed. IRB approval of the protocol and the informed consent form must be given in writing.

The Investigator(s) must receive a copy of the letter of approval from the IRB, which specifically approves the protocol and informed consent, before participant enrollment. The IRB must also approve any significant changes to the protocol and documentation sent to the Investigator(s). The IRB must review the research project at least once every 365 days during the project. Continuing approval of the project must be given in writing and provided to the Investigator(s).

Records of all study review and approval documents must be kept on file by the Investigator and are subject to inspection during or after completion of the study. Adverse events must be reported to the IRB according to local procedures. The IRB should receive notification of completion of the study and final report within 3 months of study completion and termination. The Investigator will maintain an accurate and complete record of all submissions made to the IRB, including a list of all reports and documents submitted. The Investigator will grant monitor(s) and auditor(s) from the NCI and regulatory authorities access to the participants' data. Participants confidentiality will be maintained and will not be made publicly available to the extent permissible by the applicable laws.

As detailed below

- Persons must have provided informed consent to participate in the study;
- All participant data must be handled and stored securely;
- Study risks will be reduced with adequate protections from risks;
- Participants will be monitored for adverse events;
- A Data and Safety Monitoring Board will monitor participant welfare.

Institutional Review Boards (IRB) at UChicago, UTHealth, and MD Anderson will receive approval for their protocols and consents and then submit those approved documents to the Principal Investigator who will include these documents in an IRB application at MCW. Once MCW has approved the full study protocol, recruitment can begin. All persons working with participants or participant data will have relevant human protections training.

### **Informed Consent Process**

The process for obtaining informed consent will use a video conference or a phone call to a person with a smart phone. Persons who do not have access to this technology will be consented in person.

At the beginning of the electronic consent meeting (pre-arranged by appointment), staff will ask participant to confirm email address and name and then use REDCap to send the person a link by email or text (depending upon technology used by the person). Person will click on the received link to open the ICF in REDCap. Receipt of the unsigned ICF on the computer/tablet or smart phone, will be confirmed by the participant before beginning the consent session. With delivery of REDCap electronic versions of the ICF, both study staff and participant will now be viewing the study ICF. Study staff will explain study procedures, risks, benefits, confidentiality. Prior to signature, the staff member will ask the participant if they have any questions and, if not, to briefly review their understanding of their participation to be sure the information was clearly understood. The person obtaining consent will emphasize that participation is voluntary and that participants can choose to join or, if they do join, leave the study at any point without any repercussions. Study staff will frequently refer to pages, headings or some other marker in the ICF to make sure the participant is following along.

Persons agreeing to provide consent will sign the ICF as follows: a. Touch screen - persons will use finger or mouse to sign; b. No touch screen - persons will use a mouse to sign. After signing, person will submit by clicking on/touching the "Submit" button on the REDCap screen displaying the ICF. REDCap has two settings to send signed ICFs to participants and both will be employed to allow participants to have their choice of either downloading a pdf of the signed ICF or receiving an email with signed ICF attached.

For consents in person, the participant's identification is checked when coming to the consent face-to-face meeting. When a participant appears for an appointment, they will be thoroughly informed of all study procedures, potential risks, benefits, and that one can discontinue participation in the study at any time without risk to subsequent care at the place(s) where health care is received, etc.

Participants in couples must both consent to the study to be enrolled as partners. They can be consented together.

### **Use and Access of Protected Health Information (PHI) and Retention of Records**

The primary platform for collection of all study data is REDCap (REDCap, Vanderbilt University) which will store data on a secure internet-based server. REDCap meets Health Insurance Portability and Accountability Act privacy standards for health records. Study PCs will have passwords and strong data encryption installed as per requirements at MCW.

Staff will collect participant contact information such as email address, telephone number, and mailing address to send study reminders and to share study-related updates. Staff will also collect information about secondary contacts to support study retention if initial contact information is no longer valid. Staff will not collect social security numbers.

All other study data will be coded only with a Study ID. Personal identifiers such as name, address and phone number will be removed from clinical results. The computer-assisted self-interviews will be identified only by ID number and do not contain personal identification information. Information linking the participants' identity to the study code will be kept in a Linking Log on a secure server. Separate cabinets will contain informed consents.

CASI data will be delivered directly from tablets and PCs in Chicago and Houston to MCW servers using REDCap. Clinician and participant data from clinic visits will be collected in hard copy and then entered into REDCap. Qualitative interview data will be collected in hard copy and by audio recordings on study computers. Audio recordings will be transcribed with both recordings and transcriptions stored on MCW servers. Original hard copies of all data will be stored in locked file cabinets separate from linking logs and consents.

After all study queries and analyses are completed, the data/PHI will not be destroyed but will be archived in a secure long-term storage site to keep an accurate record of screened and enrolled subjects for the sponsor and potential audit purposes only specific for this study. No information that could lead to personal identification of participants will be included in any of the reports or given to any non-authorized person. Staff will store the identified information for 10 years after study completion, as required by the NIH. Staff will destroy all personal identifiers after analyses are completed.

### **Risks to the Subjects**

The risks to participants can be divided into four groups: a) risks during the health care provider DAREs, b) risks during collection of anal canal exfoliated cells, c) risks during the ASE/ACE, and d) concerns about disclosure of confidential, sensitive information.

- a) Each health care provider will perform a DARE on the participant which will entail inserting a gloved finger into the anal canal. While this is a common and safe procedure, it may be mildly uncomfortable or embarrassing for some participants.
- b) Collection of anal canal cells: Some persons may feel embarrassed about a health care provider inserting a swab into the anal canal. The swab can be uncomfortable, and occasionally there can be some bleeding. Justification: Currently there is no acceptable anal cancer biomarker. These specimens will be archived and then available for testing of candidate biomarkers.
- c) The participant will perform an ASE/ACE which will entail the participant looking at the perianal region (individuals will use a mirror or selfie) and then inserting a gloved finger into their own anal canal or that of their partner. While it is common for a person to insert a finger into the anus or the anus of another while having sex or engaging in exploration or self-hygiene, it may be uncomfortable or embarrassing for some participants. Partners will ask each other for

consent before performing the procedure. If an anal fissure is present, finger insertion could be more painful. It is also possible that a participant will palpate a mass which may induce anxiety, e.g. if the participant imagines that the mass could be a malignant tumor. This risk is justifiable because the participant will, at the same visit, meet with a health care provider who completes a DARE on the participant and who can explain the results and support onsite treatment or referral for treatment if needed.

d) This study will ask sensitive questions about sexual behavior and disease status. Some people may fear that unauthorized persons, who may discriminate, might obtain this information or otherwise cause a change in the participant's social status or access to benefits to which participants would otherwise be entitled. In addition, some persons who do a qualitative interview may feel uncomfortable talking about their ASE/ACE experience. This information is needed to better understand how to modify instruction in the procedures to reduce false-negatives and false-positives, and how to support health care engagement for true-positives. The study team will do everything possible to protect subjects' confidentiality.

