### **Adverse Event Reporting**

Expected and unexpected adverse events will be reviewed by the research team on a weekly basis. We expect this study to be of minimal risk since all activities are already commonplace and routinely used in clinics globally.

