### **Data and Safety Monitoring Committee**

The MCW Cancer Center's Data and Safety Monitoring Committee (DSMC) will monitor this study. The DSMC will help ensure the safety of the participants by monitoring adverse outcomes throughout the study and by reviewing outcome data for possible harm. The DSMC will pay particular attention to the potential for severe anxiety in participants who believe they may have palpated a malignant disease in their anus.

The table below specifies which adverse events (AEs) and serious adverse events (SAEs) should be reported to the DSMC and when they should be reported. An SAE is defined as an adverse event that (1) results in death, (2) is life-threatening, (3) requires inpatient hospitalization or prolongation of existing hospitalization, (4) results in persistent or significant disability/incapacity, (5) results in a congenital anomaly/birth defect, or (6) is an important medical event that jeopardizes the subject or requires medical intervention to prevent one of outcomes listed above. Adverse events will be graded according to CTCAE v5.

Attribution	SAE				AE		
	Grade 1, 2, and 3		Grade 4 and 5		Grade 3	Grade 4	
	Expected	Unexpected	Expected	Unexpected	Unexpected	Expected	Unexpected
Possible Probable Definite	Not required to be reported	Within 5 calendar days 	Within 5 calendar days 	Within 5 calendar days 	Routine reporting 	Within 5 calendar days 	Within 5 calendar days 
Unrelated Unlikely	Not required to be reported to DSMC						
 For expedited (within 5 calendar days) DSMC reporting, the study coordinator must notify the DSMC via email including the subject ID, date of event, grade, relatedness, expectedness, and a short narrative. The event should also be entered on the Adverse Event Log.  For routine reporting, events should be entered onto the Adverse Event Log for review at the time of DSMC scheduled monitoring.							

Please note that the above guidelines are for the DSMC only. SAEs also need to be reported to the IRB, and participating sites should follow their IRB's institutional guidelines for reporting.

A running log of deviations should be kept and reported to the DSMC at time of scheduled monitoring. Any deviations requiring immediate reporting to the IRB should also be reported to the DSMC immediately.

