Any other events requiring immediate reporting to the IRB (e.g., Unanticipated Problems Involving Risk to Subject or Other) should also be reported to the DSMC immediately.

A summary of the MCWCC DSMC activities are as follows:

- Review the clinical trial for data integrity and safety.
- Review any adverse events as specified above, as well as deviations.
- Submit a summary of any recommendations related to study conduct to the PI.
- Terminate the study if deemed unsafe for participants.

The committee will review the study for scheduled monitoring after completion of 100 of participant visits and at six-month intervals thereafter (or more frequently if needed) and provide recommendations on trial continuation, suspension or termination as necessary. Any available DSMC letters will be submitted to the IRB of record as required.

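### The DSMC is asked to watch for severe anxiety after palpation, but its reporting table has no column for an expected, non-serious Grade 3 event

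*Combined protocol and SAP*

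**What the plan says.** Risks to the Subjects, item (c), foresees the harm: "It is also possible that a participant will palpate a mass which may induce anxiety". It accepts the risk on one ground: "This risk is justifiable because the participant will, at the same visit, meet with a health care provider who completes a DARE".

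The Data and Safety Monitoring Committee section gives the committee a specific duty: "The DSMC will pay particular attention to the potential for severe anxiety in participants who believe they may have palpated a malignant disease". It then sets the reporting rule: "The table below specifies which adverse events (AEs) and serious adverse events (SAEs) should be reported to the DSMC". The table is split by seriousness, CTCAE v5 grade, expectedness and attribution. The lighter of its two reporting routes is described as follows: "For routine reporting, events should be entered onto the Adverse Event Log for review at the time of DSMC scheduled monitoring".

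The same section gives the committee a broader task of "reviewing outcome data for possible harm". Its closing list of activities describes the adverse event review this way: "Review any adverse events as specified above, as well as deviations".

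Adverse Event Reporting describes a separate review that is not the committee's: "Expected and unexpected adverse events will be reviewed by the research team on a weekly basis".

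**The concern.** A duty to watch for a named harm needs a route by which cases of that harm arrive. Here the committee's duty and its reporting table do not meet. The protocol foresees anxiety in two places, so staff completing a report could reasonably class it as expected. The table then brings it to the committee only at Grade 4 or above. If severe is taken to mean Grade 3, the committee could come to a scheduled review and find no such event on the log although some had occurred.

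The committee can stop the study if it judges participants to be unsafe, so what reaches it matters. If sites are left to decide expectedness for themselves, one could log an event that another leaves off.

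**Working it through.** No sample size, power or alpha figure is involved. The check is a reading of the table against the text around it.

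**Step 1. Is the table complete as read?** Header cells: SAE Grades 1–3 (expected, unexpected), SAE Grades 4–5 (expected, unexpected), AE Grade 3 (unexpected), AE Grade 4 (expected, unexpected). That is 2 + 2 + 1 + 2 = 7. The row for possibly, probably or definitely related events has 1 entry of no reporting required, 5 of reporting within 5 calendar days and 1 of routine reporting: 1 + 5 + 1 = 7. Headers and entries match, so a column lost when the PDF was read is unlikely.

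**Step 2. What happens to a related event?**

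| Event | Expected | Unexpected |
|---|---|---|
| AE, Grades 1–2 | no column | no column |
| AE, Grade 3 | **no column** | routine (log) |
| AE, Grade 4 | 5 calendar days | 5 calendar days |
| SAE, Grades 1–3 | not required | 5 calendar days |
| SAE, Grades 4–5 | 5 calendar days | 5 calendar days |

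A related, non-serious, Grade 3, expected event has no cell. Change any of three attributes and the result differs: unexpected goes on the log, Grade 4 goes within 5 days, and serious at Grades 1–3 while expected is expressly exempt.

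**Step 3. Is anxiety expected?** Item (c) of Risks to the Subjects and the DSMC section both name it in advance, which makes expected its natural class. The reviewed text contains no list of expected events to confirm this.

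**Step 4. Does another route reach the DSMC?**
- Adverse Event Reporting: the weekly review covers expected events but belongs to the research team.
- Protections against risk: the nurse practitioner treats or refers any reported adverse event and sends the documentation to the principal investigator and co-investigators within 24 hours, with NIH reporting where appropriate. The DSMC is not named.
- DSMC section, closing list: the adverse event review points back to the table.
- DSMC section, opening: outcome data are reviewed for harm, but nothing says this includes the anxiety levels that staff record at practice follow-up calls (Between Visit 1 and Visit 2 study procedures).
- DSMC section, last reporting rule: events needing immediate IRB reporting also go to the DSMC. Nothing says that non-serious, expected Grade 3 anxiety is among them.

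**Step 5. Does the same-visit justification fit every exam?** At Visit 1, yes: the DARE and the self- or companion exam share one clinic visit. At Visit 2 the exam is done at home within 24 hours before the clinic DARE (Preparation for Visit 2). The Arm 1 practice exam, three months after Visit 1, has no visit attached; it is covered by a staff call and a request to return. The sentence is accurate for Visit 1 only.

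**The case against.** The strongest reply is that the gap needs four conditions at once: the event must be related, Grade 3, non-serious and classed as expected. The fourth is inferred. The protocol foresees anxiety, but that does not make severe anxiety an expected event. The consent form and coordinator forms appear only as appendix headings because such pages were removed before review, and a list of expected risks may be there. This stands, and the conclusion is therefore conditional.

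The committee's remit is also wider than the table. It reviews the trial for safety in general, and anxiety is study data in the exploratory interviews at Visit 1 as well as at practice calls. A committee that took its instruction seriously could ask for those data. That is fair, but it relies on the committee asking; the only reporting rule written down leaves this event out.

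A reader might infer that severe anxiety after an exam would go unseen or unmanaged. The documents do not support that. In the practice arm, staff make the follow-up calls and ask about anxiety and pain, and the threshold for asking a participant back to the clinic is far below severe. Training tells participants that a mass need not be cancer. At Visit 2 a clinician's DARE, with results given at once, follows within 24 hours. Any reported adverse event reaches the investigators within 24 hours. What is missing is the step from the investigators to the DSMC.

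A reader might also infer that anxiety is the only harm the committee monitors, or size the gap by counting exams without a DARE at the same visit. Neither holds. The committee monitors adverse outcomes throughout and gives anxiety extra weight. A count of exams is not a count of severe anxiety events.

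**Conclusion.** The point holds as a minor, conditional one. Followed as written, the table can keep off the committee's log the harm that the same section singles out for attention. The size is one missing cell. The number of affected events cannot be derived from the documents, and no estimand, endpoint or analysis changes.

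The conclusion rests on two assumptions: that severe means Grade 3, and that foreseen anxiety is classed as expected. If such events are graded 4, or classed as unexpected, the table already captures them. If an expected-event list in the removed pages settles the class as unexpected, the gap closes for this harm.

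The same-visit sentence in item (c) is a secondary matter of wording. It no longer describes the exams outside Visit 1, but other sections largely supply the safeguards for those.

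**What to change.** 1. Add one line to the DSMC reporting table: Grade 3 anxiety after any self- or companion exam (Visit 1, practice or Visit 2) that is possibly, probably or definitely related is entered on the Adverse Event Log for scheduled DSMC review, whether expected or not. Leave the Grade 4 and 5 rules as they are.
2. Give the DSMC, at each scheduled review, a summary of the anxiety levels already recorded at practice follow-up calls. The study timeline ends in the second quarter of 2023 and version 4.5 was approved on 12/20/2023, so visits may be complete. In that case do this once from the recorded data.
3. As a wording correction, limit the justification in item (c) to Visit 1. For the other exams, cross-refer to Between Visit 1 and Visit 2 study procedures, Preparation for Visit 2, Visit 2 Study Procedures and Protections against risk.

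The cost is a little extra logging, some additional reading for the committee and a short protocol edit. Participants face no new procedure, and the summary uses data already collected.
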